Oral alkali replacements are readily available, safe and include the following formulations sodium bicarbonate, BiCitra (sodium citrate and citric acid), PolyCitra (citric acid, sodium citrate, and potassium citrate), polycitra-K (potassium citrate and citric acid). In contrast to sodium bicarbonate, citrate is converted to bicarbonate in the liver and thus this conversion is affected by liver disease. Usual adult doses for urinary alkalinization are 325 to 2000 mg orally 1 to 4 times a day. One gram provides 12 mEq (mmoL) each of sodium and bicarbonate, and is titrated to a goal of urine pH of 8.0. In a prospective open-label trial 4 g of sodium bicarbonate was administered orally 3 times daily to 9 healthy volunteers for 24 hours, and after 10 hours all participants had a urine pH \ge 7 and after 20 hours all participants had urine pH \ge 8. No adverse effects or abnormal blood results were documented during the 24-hour follow-up (16). Urinary alkalinization should solubilize UUA thereby increasing the concentration of uric acid in urine and decreasing precipitation and crystallization in type 1 diabetes.

With diabetic nephropathy being the leading cause of end-stage renal disease in the Western world. Novel therapeutic targets could help halt the progression of kidney disease in people with type 1 diabetes, thereby improving morbidity and mortality, and lessen the public health burden. While the currently available therapies focus on the glomerular injury of diabetic kidney disease, urine uric acid crystallization is associated with tubular injury, and is thought to precede the onset of glomerular disease in type 1 diabetes. Earlier interventions could decrease the rate of renal function loss and prolong the time to development of end stage renal disease. UUA is a particularly attractive therapeutic target due to the potential to reduce tubular injury with sodium bicarbonate. Furthermore, the ongoing Prevent Early Renal Loss (PERL) study with \$27 million in NIH funding will determine if lowering uric acid with allopurinol slows decline in renal function, and sodium bicarbonate to alkalize urine could be a complementary, safe and cheap treatment. Accordingly, we propose a pilot experimental study examining the effect of urine alkalinization with oral sodium bicarbonate on UUA precipitation and crystallization in adults with type 1 diabetes.

III. Preliminary Studies/Progress Report:

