Labs methods: Serum creatinine, serum cystatin C, serum uric acid and serum glucose will be determined using standard methods in the CTRC core lab and [name]'s lab. Urine uric acid, urine glucose, urine creatinine and urine pH will be measured at [name]'s lab. Urine ketones will be checked at BDC.

Sample banking: Residual blood and urine volume will be stored for future research, in particular to use when new and promising urinary and serum biomarkers become available.

Sodium bicarbonate: Three tablets of 650mg of sodium bicarbonate (1950mg) will be given twice a day to all participants. [name] Pharm.D. will arrange and dispense medications. Prescriptions will be written for the dose to be taken by the participants at home.

Other forms: Standard medical history will be obtained (see accompanying forms in submission packet).

Estimation of GFR: Various equations have been developed to estimate GFR based on either serum creatinine or cystatin C plus other variables. We will employ the state of the art CKD-EPI combined creatinine and cystatin C to calculate estimated GFR in our participants.

CKD-EPI combined creatinine and cystatin C eGFR = eGFR = 135 x min(serum creatinine/k, 1)^{-a} x max(serum creatinine/k, 1)^{-0.601} x min(serum cystatin C/0.8, 1)^{-0.375} x max(serum cystatin C/0.8, 1)^{-0.711} x 0.995^{age} [x 0.969 if female] [x 1.08 if black]

Compliance:

To improve compliance, the first dose of sodium bicarbonate (1950 mg) will be administered at the visit #2 at CTRC. Moreover, participants will be asked to set an alarm on their phone for the second and final dose (1950mg) at home.

Plan to minimize risk:

1. Fasting and hypoglycemia:

Fasting will be limited to 8 hours, and detailed fasting and insulin instructions will be given to participants.

2. Venipuncture to draw blood for lab tests:

Venipuncture will be performed by research personnel with experience with venipuncture to reduce risk of pain. Gloves will be worn and the area of skin cleaned to prevent risk of infection.

3. Sodium bicarbonate administration:

The study participant will be monitored for a minimum of an hour after the administration of the first sodium bicarbonate dose to check for any reaction. The study participant will be told to call with any issues or concerns at home. Participants taking medications known to interact with sodium bicarbonate will be excluded from participating.

E. Potential Scientific Problems:

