In any clinical study unforeseen human factors provide challenges. The current study is based upon a previous study with sodium bicarbonate administration in adults with no reported adverse effects. Furthermore, we aim to use lower doses of sodium bicarbonate in this study. We have also performed careful power analyses to allow meaningful analyses.

F. Data Analysis Plan:

(A HIPAA compliant, Red Cap database system will be used for this study.)

| Outcome | Effect size | SD pre and post | Correlation of pre with post | SD of change | Power | Ν |
|--------------------|-------------|--------------------|------------------------------------|-----------------|-------|----|
| Urine pH | 0.5* | 0.42 | 0.5 | 0.42 | >99 | 20 |
| | 1.0* | 0.42 | 0.5 | 0.42 | >99 | 10 |
| Urine uric acid | 10% | 16.48 | 0.95 | 5.21 | 80 | 47 |
| | 20% | 16.48 | 0.80 | 10.42 | 80 | 47 |

Table 1 Power calculations:

* Units on the pH scale

Per our power analysis, with a sample size of 50 we will have power of 0.8 to detect effect size of 20% change in urine uric acid following 24-hours of NaHCO₃. Paired t-test will be employed to evaluate whether the change in urine uric acid pre- and post NaHCO3 administration is statistically significant. We will also adjust for covariates with ANCOVA or linear regression models [ANCOVA vs. linear regression models will be decided based on the variation of urine uric acid at baseline in our participants].

We will also calculate fractionated excretion of uric acid (FeUA = [(UUA * SCr / SUA * UCr)*100]), and regress FeUA, SUA and UUA on eGFR calculated by CKD-EPI creatinine and cystatin C. Furthermore, we will also regress blood glucose and urine glucose on FeUA, SUA and UUA.

G. Summarize Knowledge to be Gained:

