Diabetic nephropathy remains the leading cause of end-stage renal disease and dialysis in the US. While diabetic glomerulopathy has received significant attention from researchers and clinicians, determinants of tubulointerstitial injury in diabetes are less well examined. Compared to glomerular injury, tubular injury is known to associate better with renal function in diabetes (2). In fact, tubular proteinuria may precede microalbuminuria with type 1 diabetes (3), suggesting that tubular damage may be induced earlier than glomerular injury in the course of diabetic nephropathy. Animal studies have demonstrated that blocking uric acid production protects the kidney from tubulointerstitial injury, which suggests a causal role for uric acid in the development of diabetic tubular injury (9, 10). Acidification of urine is associated with urine uric acid crystallization which may lead to tubular injury (11, 12). For that reason, urine alkalinization with sodium bicarbonate is a safe and potentially effective therapy to increase solubility of urine uric acid and prevent crystallization and associated tubular injury. Urine alkalinization could potentially prevent or halt progression of diabetic nephropathy in type 1 diabetes.

H. References:

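### The protocol calls the treatment safe on event data of 0 in 9 healthy volunteers, and describes no systematic questioning about, or summary of, adverse effects after the home dose

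*Combined protocol and SAP*

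**What the plan says.** **The safety statements.** Section II opens its paragraph on treatment with a class statement: "Oral alkali replacements are readily available, safe and include the following formulations". The same section later presents sodium bicarbonate as a safe and inexpensive complement to allopurinol. Section IV.G concludes that "urine alkalinization with sodium bicarbonate is a safe and potentially effective therapy". There *effective* is qualified by *potentially*, while *safe* is not qualified.

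**The evidence cited.** Section II describes a prospective open-label trial in which "4 g of sodium bicarbonate was administered orally 3 times daily to 9 healthy volunteers for 24 hours", and reports: "No adverse effects or abnormal blood results were documented during the 24-hour follow-up". Section IV.E relies on it: "The current study is based upon a previous study with sodium bicarbonate administration in adults with no reported adverse effects". The protocol also cites customary dosing ("Usual adult doses for urinary alkalinization are 325 to 2000 mg orally 1 to 4 times a day"), a lower total dose than that trial used, and exclusions for hypocalcemia risk and interacting drugs. It gives no event counts for any of these.

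**What is planned in this trial.** Section IV.D (Plan to minimize risk, item 3) has participants observed for at least an hour after the first dose for a reaction. For the time at home it says: "The study participant will be told to call with any issues or concerns at home". The Study Visit #2 paragraph in Section IV.C lists fasting, urine and blood. Section IV.A names only urine uric acid outcomes, and Section IV.F analyses no adverse events.

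**The concern.** An unqualified safety statement should rest on event data, and the only data shown are a zero count in nine people without type 1 diabetes. The trial will treat several times that number of people from the target population, so it could replace that thin evidence with its own. As described, it would not. The active check ends about an hour after the first of two doses. The rest of the roughly 24-hour exposure, including the home dose about 12 hours later, depends on participants deciding to call.

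Unsolicited reporting tends to undercount mild events. Without a question put to everyone, no reported events cannot be told apart from no events. A later, longer study that cites this pilot would then have no usable count to cite.

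**Working it through.** **Inputs**

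- Earlier trial: 0 events in n = 9, 4 g three times = 12,000 mg in 24 hours (Section II).
- This trial: 2 x 1,950 = 3,900 mg in 24 hours, single arm (Sections IV.C and IV.D). Dose ratio 3,900 / 12,000 = 32.5%.
- Planned size: 47 (Section IV.B and Table 1) or 50 (Section IV.F text).
- Recruitment: 78 adults, 80% eligible, 60% of those consenting (Section IV.B).

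**Step 1: the plan's own figures.** The protocol states no adverse-event rate, bound or safety-based sample size, so there is none to reproduce. The 47 comes from the urine uric acid calculation and serves here only as a denominator. Section IV.B's recruitment rates do not deliver it: 78 x 0.80 x 0.60 = 37.4. Leaving out the eligibility factor gives 78 x 0.60 = 46.8. Both 37 and 47 are therefore carried forward.

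**Step 2: upper limit when no event is seen.** For 0 events in n, the exact limit solves (1 - p)^n = a, so p = 1 - a^(1/n). Here a = 0.025 for a two-sided 95% interval and 0.05 for a one-sided 95% limit.

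| n | Two-sided 95% | One-sided 95% |
|---|---|---|
| 9 (earlier trial) | 1 - 0.025^(1/9) = 33.6% | 1 - 0.05^(1/9) = 28.3% |
| 37 | 9.5% | 7.8% |
| 47 | 7.5% | 6.2% |
| 50 | 7.1% | 5.8% |

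Questioning everyone and finding nothing would lower the two-sided limit by a factor of 33.6 / 9.5 = 3.5 (37 participants) to 33.6 / 7.5 = 4.5 (47 participants).

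**Step 3: how easily 0 of 9 arises.** With a true rate of 10%, 0.90^9 = 0.387. With 20%, 0.80^9 = 0.134. A rate of one in ten would therefore leave nine volunteers event-free 39% of the time.

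**Step 4: chance of seeing at least one event when the true rate is 5%.**

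- n = 9: 1 - 0.95^9 = 37%
- n = 37: 1 - 0.95^37 = 85%
- n = 47: 1 - 0.95^47 = 91%

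These apply only if every dosed participant is asked.

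**Step 5: what the plan covers, period by period.**

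| Period | Method described |
|---|---|
| First hour after dose 1 | Active observation (Section IV.D) |
| Remainder, including the home dose | Participant-initiated call (Section IV.D) |
| Final visit | Urine and blood; no symptom question (Section IV.C) |
| Analysis | No adverse-event summary (Section IV.F) |

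The first row is itself unsettled. Section IV.C gives dose 1 at visit #1, while the Compliance paragraph of Section IV.D gives it at visit #2. Section IV.C also estimates 60 minutes for a visit that includes eligibility, consent, sampling and dosing, which leaves no room for a post-dose hour.

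**The case against.** Several stronger readings are tempting, and the documents do not support them.

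- **That the protocol never asks about adverse effects.** It plans an active check after dose 1 and invites calls afterwards. Section IV.D also refers to forms in the submission packet that are not in the public text, so complete absence cannot be shown. What can be said is that nothing systematic is described after the first hour.
- **That *safe* rests on the nine volunteers alone.** The class statement in Section II comes before that trial is mentioned, and the protocol also argues from customary doses, a total dose about one third of the earlier one, and exclusions. These are fair reassurance, but they supply no counts.
- **That the trial sets out to prove safety and fails.** Safety is not an aim, hypothesis or outcome. In Section IV.G the word belongs to a rationale paragraph. On its own that would be a minor wording matter.
- **That the trial would hold no data with a denominator.** Serum glucose, creatinine and cystatin C are measured in everyone at both visits, and the first-hour check applies to everyone. They are not labelled or analysed as safety data.
- **That 34% estimates the risk of this regimen.** It is an upper limit for an undefined event at 12 g per day in healthy people. It shows how little nine people can exclude.

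There is also a fair objection to the remedy. With no control arm, and with fasting and a prescribed diet running alongside, symptom counts could not be attributed to the drug. Hypoglycemia, for example, is named in the protocol as a fasting risk. Zero events after two doses would also say nothing about prolonged use. This limits what the new table can claim, but not the value of having the count.

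**Conclusion.** The point holds in a limited form. The treatment is called safe, the only event data cited are 0 of 9 with an exact two-sided upper limit of 34%, and the plan describes neither systematic elicitation after the home dose nor any adverse-event summary. Asking everyone would bring the limit after zero events to 7.5% with 47 participants or 9.5% with 37.

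These figures assume independent participants, a common event rate, complete questioning of everyone dosed, and that the earlier trial's zero reflects adequate enquiry. The result would be uncontrolled short-term data, not proof of safety. No aim of the trial is invalidated. This is a low-cost improvement in method, and most of its value lies in the data collection. Rewording *safe* without collecting data would change little.

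**What to change.** 1. **Final visit (Section IV.C).** Ask every dosed participant a fixed symptom question, worded in advance, covering the time since the first dose, and record the answer whether positive or negative. The investigators should choose the symptoms listed, and an open item should be included.
2. **Section IV.F.** Report the number with each symptom, and with any symptom, over all dosed participants with exact (Clopper-Pearson) 95% intervals. Show separately anyone dosed but not asked, so that they are not counted as event-free. Label the table as uncontrolled, short-term data.
3. **Sections II and IV.G.** Limit *safe* to what was observed: no documented adverse effects in 9 healthy volunteers over 24 hours, with the upper limit given.
4. **Reconcile** the visit at which dose 1 is given (Section IV.C against the Compliance paragraph in IV.D), and the 60-minute visit estimate against the minimum hour of observation after dosing.

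The cost is a few minutes per participant at a visit already planned, one extra table, and less favourable safety wording. No additional participants are needed.
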